4.1 Data management

Information obtained from participants will be treated confidentially.

Files containing identifiable participant information will be stored on the Jamieson Trauma Institute server. These files and data are accessible via a Queensland Health computer at the Jamieson Trauma Institute and Research Centre, accessible only by the research team members. De-identified data will be stored on the Queensland Health password protected, secure server. Paper records will be stored in a locked fire-proof cabinet on a secure access floor of the Jamieson Trauma Institute, accessible by the members of the research team only. Patient data will be exported for analysis using SPSS (version 25.0, IBM, New York, NY, USA), and will be de-identified immediately, with each generated file password protected. If data needs to be sent between researchers and other team members in the analyses/reporting stage, these will be sent via Queensland Health email in password protected files. Data will only be accessed by and shared with researchers associated with the study. Publication of results/data will be de-identified so that the identity of participants in the study is not revealed. In line with Section 2 of the Australian Code for the Responsible Conduct of Research, research data will be retained for a period of 15 years from the date of publication. At the conclusion of this period, all the primary data will be deleted.

5.0 Withdrawal or dropout from study

Reasons for withdrawal or dropout from the study will be recorded by the research team, particularly as this information may be important for future work. Patients who withdraw or drop out of the study will be asked to return the smart devices to the research team, and no further data collection will take place.

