The **clinical outcomes** of ankle rehabilitation will be evaluated using the AFORM questionnaire (8). This is a validated outcome measure for patients with ankle impairment and has been shown to possess high validity and reliability. It is a patient reported outcome measure, which is condition specific for use in clinical and research settings among patients who suffered an ankle fracture. The A-Form is comprising of 8 questions assessing activities of daily life and sporting activities. (Appendix 4)

Additional measurements will include health related quality of life measured using the EQ-5D 5L (EuroQol five-dimension health utility tool) which will be taken at all 3 points (at 2, 6 and 12 weeks post-operatively). The EQ-5D 5L is used to measure health utility and can be used to value health services in terms of quality-of-life improvement. It is not disease-specific and therefore enables

comparison across different diseases. Health utility measures are important for cost-effectiveness analysis and data from the EQ-5D 5L will enable economic evaluation of changes to health services as a result of introducing this new technology.

Data from the Magnes device will be downloaded at each fortnightly physiotherapy appointments (Appendix 2). The Magnes device provides data in force measurements (Newtons) which will be interpreted as weight-bearing and will be plotted to show the gradual increase through the period of rehabilitation and recovery.

Baseline measurement will be taken at the first postoperative appointment at 2 weeks post-surgery. Subsequent measurements will be taken at 6 and 12 weeks. If patients miss their follow-up appointments, the research nurse will call the patient and collect the outcome measures over the phone. Sensor data will be collected on the next visit of the patient to the clinic.

Objective measurements of ankle dorsiflexion, plantar flexion, eversion and inversion will be taken by the research physiotherapist using a goniometer as per standard clinical practice.

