4.0 Data collection

Data will be collected at 2 weeks post-surgery (baseline for this study), and at 6- and 12-weeks follow-up. Non identifiable baseline data, such as gender and age, will be recorded, in addition to non-identifiable health related data, for example, date of injury, injury cause, imaging reports and type of surgery. This information will be recorded on a secure, password protected Metro North REDCap server. See Appendix 5 for a pdf of the REDCap data dictionary. Range of movement, AFORM and EQ-5D 5L: measures will be taken at each follow-up visit.

Table 1: Outcomes to be recorded at patient follow-up visits

No.	Measurement	Description	When measured
Ability to use technology: insoles and iPad App			
1.	Data upload	Has the data been uploaded to the cloud successfully for the time period in question	2, 6, 8, 10 and 12 weeks
2.	Device charging and monitoring	How long each day did the patient wear the boot/shoe? Did the device remain charged (and able to record data) for the time period in question? Were there any problems related to keeping the battery charged?	2 weeks, 6 weeks, 12 weeks
3.	Other issues raised by the patient	Description of any other problems faced by the patient that limit their ability to use the device and capture data.	2 weeks, 6 weeks, 12 weeks
4.	Ownership of a smartphone	Patients will be asked if they own a smartphone (necessary as the future randomised trial will require this)	At recruitment
Patient Reported Outcome Measures			
5.	AFORM	Standardised questionnaire, filled in by the patient.	2, 6 and 12 weeks
6.	EQ-5D 5L: EuroQol five-dimension health utility tool	Standardised questionnaire, filled in by the patient.	2, 6 and 12 weeks
7.	Return to work	Has the patient returned to work? Is the patient able to return to work?	2, 6 and 12 weeks
8.	Medication review	Consumption of OTC and prescription analgesics	Daily for 12 weeks
Other clinical measures			
9.	X-ray ankle	XR ankle: WB out of cast – AP/lateral/mortise	6 weeks
10.	Wound review	Orthopaedic Department Nurse	2 weeks
11.	Weight-bearing	Magnes Sensor Data	2-6 -8*-12 weeks

No.	Measurement	Description	When measured
12.	Complications	Orthopaedic Department Nurse	Throughout the duration of the project
Range of Motion Measures			
13.	Ankle dorsiflexion (DF)	Measured using a standard goniometer	2, 6 and 12 weeks
14.	Ankle dorsiflexion (DF) (knee to wall)	Measured using a standard ruler	2, 6 and 12 weeks

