APPENDIX 2: Rehabilitation timeline

Rehabilitation strategy

Patients will be followed up at 2, 6 and 12 weeks after their surgery (as per standard clinical care), at physiotherapy and orthopaedics department outpatient clinics at the Royal Brisbane and Women's Hospital (Brisbane, Queensland, Australia) (**Error! Reference source not found.**). Physiotherapy appointments will occur in fortnightly intervals from week 2 post-operatively. In total, patients will receive 6 sessions of physiotherapy treatment. Outcome measures will be recorded on the 1st, 3rd and 6th attendance of the patient for their physiotherapy and orthopaedic follow-up appointments (wks 2, 6 and 12 post-operatively).

[figure not shown]

Figure 2. The patient's postoperative timeline, including assessment time points.

The rehabilitation exercises that patients will be instructed to do are described in APPENDIX 2. The information booklet provided to patients will include instruction sheets with cartoons showing how to perform each of the exercises (Appendix 1). Patients will be advised as to their rehabilitation, pain relief and the Aircast boot according to the information in (Appendix 1). The wound dressings will be left intact until the first follow-up visit, 10 to 18 days after surgery.

Surgery date to 2 weeks post-surgery: Gentle walking and Elevation (**Error! Reference source not found.**)

[figure not shown]

Figure 3. The patient's postoperative timeline from surgery to assessment 1.

Aircast boot

The Aircast boot should remain on at all times and **should not be inflated during the first two weeks of the postoperative period**. During showering/bathing, the cast should be covered using a plastic bag, to ensure the boot and wound dressings do not get wet.

Charlson Comorbidity Index

Chart review version

Components of classical Charlson Comorbidity Index¹

1. Has the patient had a myocardial infarction? (MI)

- No
 Yes

Criteria: Myocardial infarction includes patients with one or more definite or probable myocardial infarction. These patients should have been hospitalized for chest pain or an equivalent clinical event and have had electrocardiographic and/ or enzyme changes. Patients with electrocardiographic changes alone who have no clinical history are not designated as having had an infarction.

2. Has the patient been hospitalized or treated for heart failure? (CHF)

- No
 Yes

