APPENDIX 5 – REDCap Data Dictionary

Confidential SMART Ankle Fracture Feasibility Study
Page 1 of 8

Demographics

Study ID _____

Date subject signed consent _____
(YYYY-MM-DD)

Age (years) _____

Gender Male
 Female

Height (cm) _____

Weight (kilograms) _____

BMI _____

Comments _____

08.06.2022 8:12pm www.projectredcap.org 

Confidential SMART Ankle Fracture Feasibility Study
Page 2 of 8

Injury Details

Date of Injury _____

Cause of Injury Motor Vehicle Accident
 Motorbike Accident
 Bicycle Accident
 Pedestrian Involved in Road Accident
 Hit by Object
 Fall < 2 metres
 Fall > 2 metres
 Sport Related Accident
 Other

Details of cause of injury if 'other' _____

Imaging Reports (XR/CT/MRI) related to Ankle # _____

Other Concurrent Injuries None
 Musculo-skeletal injury
 Organ injury
 Soft Tissue injury
 Traumatic Brain Injury
 Spinal Cord injury
 Other

Details of other injuries (if applicable) _____

Co-morbidities None
 Cardiovascular Disease
 Lung Disease
 Liver Disease
 Kidney Disease
 Cancer within the last 5 years
 Infectious Disease
 Mental Health Disorder
 Other

Details of Comorbidities (if 'other') _____

Charlson Comorbidity Index Score _____

08.06.2022 8:12pm www.projectredcap.org 

Confidential SMART Ankle Fracture Feasibility Study
Page 3 of 8

Surgery and Other Treatments

Surgical Intervention Yes
 No

Surgery Date _____

Surgery Description _____

Other Treatments Physiotherapy
 Occupational Therapy
 Other

Details of Treatments if 'Other' _____

08.06.2022 8:12pm www.projectredcap.org 

Confidential SMART Ankle Fracture Feasibility Study
Page 4 of 8

Week 2 Data

2 weeks post operatively

Date of Week 2 visit _____

AFORM Score _____

EQ 5D 5L _____

EQ 5D 5L VAS _____

Knee to Wall measurement (in mm) _____

08.06.2022 8:12pm www.projectredcap.org 

Week 6 Data

Week 6

Date of Week 6 visit _____

AFORM Score _____

EQ 5D 5L _____

EQ 5D 5L VAS _____

Knee to Wall measurement (in mm) _____

Week 12 Data

12 weeks

Date of 12 Week visit _____

AFORM Score _____

EQ 5D 5L _____

EQ 5D 5L VAS _____

Knee to Wall measurement (in mm) _____

Completion Data

Study Completion Information

Has patient completed study? No Yes

Put a date if patient withdrew study _____

Reason patient withdrew from study Non-compliance Did not wish to continue in study Other

Date of study completion _____

Was all equipment returned to RBWH? Yes No

General Comments

Comments _____

Adverse Event Report

Adverse Event Date _____

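### Section 5.0 stops all data collection for undefined dropouts as well as withdrawals, so patients who stop the device or stop attending without withdrawing consent can lose later outcomes

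*Protocol*

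**What the plan says.** Section 5.0 of the protocol covers "Patients who withdraw or drop out of the study" and says that they "will be asked to return the smart devices to the research team, and no further data collection will take place". It makes no exception for complications, questionnaires or the interview. It also says "Reasons for withdrawal or dropout from the study will be recorded by the research team", but it does not define dropout.

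Other parts of the protocol bear on the same patients:

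- **Section 2.6** requires the device back at two moments only: when the study is completed and when the patient withdraws from it.
- **Section 3.1**, on missed visits: "If patients miss their follow-up appointments, the research nurse will call the patient and collect the outcome measures over the phone". It adds: "Sensor data will be collected on the next visit of the patient to the clinic".
- **Section 4.0, Table 1**, complications row: recorded "Throughout the duration of the project".
- **Appendix 2** describes the visits at 2, 6 and 12 weeks as standard clinical care.
- **Appendix 5**, completion form. The field label and its three options read: "Reason patient withdrew from study Non-compliance Did not wish to continue in study Other".
- **Section 3.1, Aims 1 and 2** list device-related adverse events and a phone interview after the 12-week assessment as acceptability outcomes. Aim 1 selects every second participant, six in all, for that interview.

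**The concern.** Stopping the device, ceasing to attend and withdrawing consent are different events. Only the last obliges the study to stop collecting new data. Section 5.0 names withdrawal and dropout together, gives both the same consequence, and leaves dropout to the judgement of whoever completes the form.

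The study asks whether patients can use the device and find it acceptable. A patient who gives it up, perhaps because of discomfort or a wound problem, is among the most informative of the 12. If that patient is recorded as a dropout, the later A-FORM and EQ-5D 5L scores, later complications and the week-12 interview are not collected. The patients left for the exploratory comparison of loading with clinical progress and adverse events (Section 2.3) would then tend to be those who got on well with the device.

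This cannot be left to an analysis plan. The rule decides what is recorded, and no analysis recovers data that were never collected.

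**Working it through.** The protocol gives no dropout rate, complication rate or formal sample size calculation, so there is no stated figure to reproduce. The check is mainly a comparison of the text.

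**Step 1. Who falls under the stop rule?** Take two patients, neither of whom has withdrawn consent.

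| Patient | Reading A: still in the study | Reading B: dropout | Text that decides |
|---|---|---|---|
| Stops using the device, still attends | Questionnaires, range of motion and complications continue; none needs the sensor | Device returned, nothing further collected | None. Section 2.6 has no device return with continued follow-up, and Appendix 5 has no field for stopping the device |
| Stops attending | Phoned under Section 3.1 | Nothing further collected | None. No number of missed visits or failed contacts turns one into the other |

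**Step 2. Is Reading B realistic?** Appendix 5 lists non-compliance beside, and apart from, not wishing to continue. The form therefore foresees patients recorded as withdrawn for a reason other than their own wish to leave. Once so recorded, they come under Section 5.0.

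**Step 3. What would be lost (illustration).** Inputs from the protocol: 12 patients, questionnaires at weeks 2, 6 and 12, complications recorded over 12 weeks. The week of departure is an assumption, so a range is shown. Share of complication recording lost = (12 − week of departure) / 12.

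| Assumed departure | Questionnaire assessments lost | Complication recording lost |
|---|---|---|
| Just after the week-2 visit | 2 of 3 | 10/12 = 83% |
| Week 3 | 2 of 3 | 9/12 = 75% |
| Just after the week-6 visit | 1 of 3 | 6/12 = 50% |

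Each later complication that goes unrecorded is 1/12 = 8.3 percentage points of the cohort. If the patient is one of the six selected under Aim 1, 1/6 = 17% of those interviews is lost.

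**Step 4. Effect on what the study can say about complications.** Assume that no event is observed, that 0 to 4 patients are cut off, and that a cut-off patient contributes nothing, which makes this an upper bound on the loss. The two-sided 95% exact upper limit is 1 − 0.025^(1/n). The chance of seeing at least one event at an assumed true rate of 10% is 1 − 0.9^n.

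| Cut off | n | Upper limit after 0 events | Chance of at least 1 event |
|---|---|---|---|
| 0 | 12 | 26.5% | 71.8% |
| 1 | 11 | 28.5% | 68.6% |
| 2 | 10 | 30.8% | 65.1% |
| 3 | 9 | 33.6% | 61.3% |
| 4 | 8 | 36.9% | 57.0% |

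The loss of precision per patient is modest. Selection matters more, because those cut off are likely to be the ones with device problems.

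**The case against.** A reader might infer that Section 5.0 flatly contradicts the phone rule and the complications row, and that it cuts off safety follow-up in everyone who merely stops the device. The documents do not support that.

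- The phone rule concerns missed appointments and expects a next clinic visit, so it addresses patients still in the study. Section 5.0 addresses patients who have left it. The two can stand together.
- Table 1 lists what is recorded at patient follow-up visits. Its complications row can be read as covering enrolled participants only.
- Nowhere is stopping the device or missing a visit equated with dropping out. Table 1 itself expects charging and usage problems to be reported at weeks 2, 6 and 12, within follow-up. The non-compliance code gives a reason for withdrawal; it does not turn non-use into withdrawal.
- The event that makes a patient leave is not lost. The reason is recorded, and Appendix 5 contains an adverse event form. Only later events are at risk.
- If a patient stops coming to clinic, the missing week-6 X-ray results from non-attendance, not from Section 5.0.
- Ending collection after withdrawal of consent is correct. The clinical comparisons are exploratory, and the study does not test effectiveness.

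All of this stands, and it removes any claim of contradiction or certain loss. It does not supply the missing definition. Section 5.0 is an operative instruction without exceptions, and the text leaves open which patients it reaches.

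**Conclusion.** The point holds as a badly drawn boundary. One stop rule serves both withdrawal and undefined dropout, and the data dictionary allows a patient who has not withdrawn consent to be recorded as withdrawn. Such a patient can lose later A-FORM, EQ-5D 5L, complication and interview data, depending on how staff classify the case. The text permits this loss but does not make it certain.

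The size depends on assumptions that the protocol does not settle. With an assumed departure at week 3, 2 of 3 questionnaire assessments and 75% of complication recording would be lost. With one later complication missed, the observed rate in 12 patients falls by 8.3 percentage points. The number of such patients is unknown. The point deserves a change because it touches the study's own acceptability outcomes and is cheap to correct.

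**What to change.** Reword Section 5.0 so that the end of data collection applies only to withdrawal of consent, from the date of withdrawal. Then state what happens otherwise:

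1. **Stops using the device, stays in the study.** The device is returned and all outcomes that do not need the sensor continue to week 12, including the interview where the patient is selected. Section 2.6 should allow device return in this case.
2. **Misses visits or stops attending.** The phone rule of Section 3.1 applies, and complications are taken from routine records where consent allows.

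In Appendix 5, align the reasons for withdrawal with these states: separate stopping the device, with its date and reason, from withdrawal of consent, and do not let non-compliance alone end follow-up. Say in Table 1 which patients the complications row covers.

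The cost is a protocol amendment, matching consent wording, a small change to the database form and a few extra calls. The clinic visits are standard care and the phone route already exists. The consent pages are not available here, so whether the present consent covers use of routine records could not be checked.

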6.0 Risks and Benefits

This study is not changing any aspect of standard clinical practice in the treatment and rehabilitation of ankle fractures so there is no additional risk from participating. The only additional burden is that the participant will complete two questionnaires at three timepoints and they will be required to charge the Magnes device once a day. There will be no direct benefit to individuals as a result of participating in this study. However, they will indirectly contribute to advances in ankle fracture rehabilitation practices, and in streamlining aftercare in this population. Participants will not be reimbursed for their time.

APPENDIX 1: Rehabilitation protocol

Ankle Fracture - Post operative Physiotherapy

The following is a guide only, please check for any changes or variances as indicated by your surgeon's post-operative plan.

(Excludes tibial plafond fractures and large posterior malleolar fractures)

0 to 2 weeks Gentle walking and elevation PWB

- Physiotherapy review post operatively for crutches
- Apply air-cast boot in theatre after surgery – No inflation
- **PWB (partial weight bear)** in air-cast boot with crutches is ok
You may opt to NWB (non-weight bear) due to pain, this is ok too.
After 3-5 days start to try and take some weight (<50% of your weight) on your

foot with the boot

- Keep boot on at all times - leave on 24/7 but check your skin underneath by undoing daily to view your skin by removing the front panel
- Rest and elevate to allow for wound healing – aim to keep your leg elevated 23hrs/day
 - When sitting elevate your leg on a foot stool, chair or up on sofa
 - When lying down, you can elevate your leg on a single pillow
 - Don't walk too much, aim for essential walking within your home in the first week
- Do not get dressings wet – cover your lower leg in a cast bag for showering
- Leave dressings intact for 10-14 days - until the '2 week' follow up
- Around 2 weeks you will have dressing removed and wound reviewed by a doctor
- A tubi-grip will be applied and the air-cast boot re-applied
- Teach application of air-cast boot – **but not to inflate for first 2weeks** and until dressing removed

Video demo: <https://www.youtube.com/watch?v=XnBm68oTDOw>

Crutches PWB = Partial Weight Bear

= <50% of your body weight

Boot on at all times

- Aim for ankle in neutral (90°)
- Can be refitted if needed to ensure heel down
- Or to check skin condition daily.

[figure not shown]
Walking with crutches:

- Crutches in front first, boot foot next taking **Partial weight** as pain allows (**up to 50% of your body weight**), good foot follows stepping up to (not past) operated foot (can use scales to check weight you're

2 to 6 weeks Progress more weight onto foot and start ankle movement WBAT

WBAT (weight bear as tolerated = up to full weight) in air-cast boot with crutches, boot inflated

- Boot on for all walking using 2 crutches
- You may be able to manage with 1 crutch indoors (crutch in opposite hand to foot)
- If painful or limping continue with 2 crutches
- Aim for step-through gait – Physiotherapist to review and advise
- Boot can be removed at night, but needs to be reapplied if walking to toilet
- Foot can get wet in shower – remove boot and dressings, start tubigrip at 2 weeks
- Remove boot 3x daily to allow for ROM exercises (Exercises 1,2,3 as below)

Exercise 1 – Seated Heel slide stretch

[figure not shown]
Sitting in a chair with boot off

Place foot on floor, heel flat

Slide foot backwards until stretch is felt

Hold for 10 seconds with heel on floor

Rest for 30 seconds and repeat stretch 5 times.

[figure not shown]

Exercise 2 – Seated Heel raises

Sitting in a chair with boot off

Raise heels up and down keeping toes flat

Repeat 20 times slowly, rest for 30 seconds and repeat 3 x 20.

Exercise 3 – Ankle back and forth

With boot off, move toes and ankle back and forth gently

[figure not shown]
Repeat 20 times slowly, rest for 30 seconds and

6 to 8 weeks Progress exercises and walking

FWB

- Wean air-cast boot, **FWB (Full weight bear) out of boot with crutches**, then single crutch, then no crutches

- Wear boot when outdoors until 8 weeks, can remove boot at night and when walking inside
- Exercises - Progress to FWB ROM in standing with no boot as directed by Physiotherapist

Exercise 4 – Ankle circles

Sitting with boot off

Move foot in circles, drawing circle with big toe

Both directions 10 times each = 20 circles

Rest 30 seconds and repeat 3 sets of 20

circles

[figure not shown]

Exercise 5 – Ankle Eversion / Inversion

(Side to side movement)

Aim to turn sole of foot inward then outward

Both directions 10 times each

[figure not shown]
Exercise 6 – Standing heel raises – 2 feet

Start by holding onto wall, chair or bench for balance

Rise on balls of feet slowly

Repeat 10x

Rest and repeat 3 sets of 10

[figure not shown]
Exercise 7 – Standing Ankle stretch A

Stand with affected foot back

Both knees slightly bent

Lean into wall until stretch in lower calf

Hold for 10 seconds

Exercise 8 – Standing Ankle stretch B

Stand with affected foot back

Back leg straight keeping heel on floor

Foot turned slightly out

Lean into wall until stretch in calf

Hold for 10 seconds

Exercise 9 – Single leg balance

Attempt to balance on one foot, can hold onto wall, bench to start with

Aim to stand on one foot for 5 seconds, build up to 10 seconds

Other exercises your Physiotherapist may prescribe:

Sit to stand, Mini-squats, Lunge knee to wall, Slow stepping on spot

Seated bike - boot off from 6 weeks, careful with time and effort on bike, monitor for swelling, start with 2 x 5mins slow revolutions for weeks 6-8, increase as appropriate

12 weeks+ Return to full activities

watching for swelling and pain.

- Physiotherapist will guide you back to full activities and sport
- Jogging and running as per your Drs and Physiotherapist advice
 - Start with mini-tramp, flat grass, turning/cutting drills, jumping, hopping, ball drills
 - ankle strapping as indicated

Table 3: Rehabilitation Protocol

Exercise no.	Name	Description
1.	Seated Heel slide stretch	Sitting in a chair with boot off Place foot on floor, heel flat Slide foot backwards until stretch is felt Hold for 10 seconds with heel on floor Rest for 30 seconds and repeat 10 second stretch 5 times.
2.	Seated Heel raises	Sitting in a chair with boot off Raise heels up and down keeping toes flat Repeat 20 times slowly, rest for 30 seconds and repeat 3 times 20
3.	Ankle Dorsiflexion (pull toes back)	With boot off, move toes back and forth gently Repeat 20 times slowly, rest for 30 seconds and repeat 3 times 20 repetitions

Exercise no.	Name	Description
4.	Ankle circles	Sitting with boot off Move foot in circles, drawing circle with big toe Both directions 10 times each = 20 circles Rest 30 seconds and repeat 3 sets of 20 circles
5.	Ankle Eversion / Inversion (Side to side movement)	Aim to turn sole of foot inward then outward Both directions 10 times each Rest 30 seconds and repeat 3 sets of 20
6.	Standing heel raises (both feet)	Start holding on wall for balance Rise on balls of feet slowly Repeat 10 times Rest and repeat 3 sets of 10
7.	Standing Ankle stretch A	Stand with affected foot back Both knees slightly bent Lean into wall until stretch in lower calf Hold for 10 seconds Rest and repeat 3 times 10 second stretches
8.	Standing Ankle stretch B	Stand with affected foot back Back leg straight keeping heel on floor Foot turned slightly out Lean into wall until stretch in calf Hold for 10 seconds Rest and repeat 3 times 10 second stretches
9.	Single leg balance	Attempt to balance on one foot, can hold onto wall or bench to start with Aim to stand on one foot for 5 seconds, build up to 10 seconds When comfortable, can try this with your eyes closed
10.	Sit to stand	Sit on a standard chair with feet planted on the floor and stand in one movement. Repeat 6-10 times, rest for 2 minutes and repeat for a further two sets.
11.	Minisquats (both feet)	
12.	Lunge – Knee to wall	
13.	Slow stepping on spot	
14.	Seated bike	Boot off from 6 weeks (careful with time and effort on bike, look out for swelling, start with 2 times 5 mins slow revolutions for weeks 6 to 8, increase time watching swelling and pain.

